Study Design	 within 3 months within 12 months Incidence of a MaxTack[™] Motorized Fixation device deficiency (DD) (e.g., insufficient tack penetration, loose tacks, tack(s) migration, tacker battery issue, etc.) on the day of the index procedure. Operative time for mesh fixation, defined as the time elapsed from the initiation of the mesh fixation process with MaxTack[™] to its completion. Surgeon satisfaction as assessed by Surgeon Satisfaction Questionnaire postoperatively. Length of hospital stay after minimally invasive ventral hernia repair procedure where the MaxTack[™] Motorized Fixation Device was used for fixation. Change in subject-reported pain at the hernia site evaluated with Numeric Rating Scale (NRS) score from 0 to 10 at screening and compared to the following timepoints: at Month 1 at Month 12 Change in subject Quality of life (QoL), as measured through the administration of the Hernia Quality of Life (HerQLes) questionnaire, evaluated at screening and compared to the following timepoints: at Month 1
	performance and safety of the MaxTack [™] Motorized Fixation Device used for fixation in minimally invasive ventral hernia repair procedures. The study will be conducted at approximately 10 sites within the United States. However, additional sites in other regions may be added as needed to meet study objectives.
	Upon obtaining IRB/EC approvals, subjects who have signed an informed consent form and who meet eligibility criteria will be enrolled in the study. Subjects will undergo elective minimally invasive ventral hernia repair

AFFIX (MaxTack [™] Motorized Fixation Device) Clinical Investigation Plan				
MDT23014	Revision	3.0	Page 15 of 97	Medtronic
	surgery using mesh for reinforcement. The procedure will utilize the MaxTack [™] Motorized Fixation Device for mesh fixation and evaluations will be conducted at various time points, including Screening, Operative, Discharge, and postoperative visits at Month 1, Month 3, and Month 12.			
	The study duration is estimated to be approximately 13 months of recruitment followed by a 12-month postoperative follow-up period (+ 45 Days). The primary analysis will be conducted when all subjects have completed their Month 3 follow-up visits (or exited the study) and may be used for regulatory and publication purposes. The final analysis, intended for comprehensive assessment, will be conducted when all subjects have completed their Month 12 follow-up visit and / or exited the study.			

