5.2.2 Secondary Endpoints

The secondary endpoints will include:

- Incidence of Surgical Site Occurrence (SSO) which are the following Adverse Events (AEs) related to the study device, mesh, and / or study procedure and defined as Seroma, Hematoma, Surgical Site Infection (SSI), bleeding at tack implantation site following the MaxTack[™] Motorized Fixation Device used for fixation in minimally invasive ventral hernia repair procedures at the following timepoints:
 - by Discharge
 - o within 1 month
 - within 3 months
 - within 12 months
- Incidence of SSO requiring Procedural Intervention (SSOPI), which are the following AEs related to the study device, mesh, and/or study procedure and defined as Seroma, Hematoma, Surgical Site Infection, bleeding at tack implantation site following the MaxTack[™] Motorized Fixation Device used for fixation in minimally invasive ventral hernia repair procedures at the following timepoints:
 - by Discharge
 - o within 1 month
 - o within 3 months
 - o within 12 months
- Incidence of hernia recurrence following the MaxTack[™] Motorized Fixation Device used for fixation in minimally invasive ventral hernia repair procedures. The evaluation of hernia recurrence will be performed via a Valsalva maneuver during a physical examination and confirmed per site standard of care medical imaging, if necessary, at the following timepoints:
 - \circ within 1 month
 - o within 12 months
- Incidence of hernia recurrences resulting in reoperation, defined as an operative procedure performed with the specific goal of repairing the recurrent hernia, at the following timepoints:

- o within 1 month
- \circ within 3 months
- within 12 months
- Incidence of MaxTack[™] Motorized Fixation Device deficiencies (e.g., insufficient tack penetration, loose tacks, tack(s) migration, tacker issue battery etc.) on day of the index procedure.
- Operative time for mesh fixation, defined as the time elapsed from the initiation of the mesh fixation process with MaxTack[™] to its completion
 - Surgeon satisfaction as assessed by Surgeon Satisfaction Questionnaire postoperatively.
 - Length of hospital stay after minimally invasive ventral hernia repair procedure where the MaxTack[™] Motorized Fixation Device was used for fixation.
- Change in subject-reported pain at the hernia site evaluated with Numeric Rating Scale (NRS) score from 0 to 10 at screening and compared to the following timepoints:
 - o at Month 1
 - o at Month 3
 - o at Month 12

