7.7 Product Accountability

The study site is responsible for maintaining the MaxTack[™] Motorized Fixation Device tracking during the study. Electronic Case Report Form (eCRF) device accountability logs must be kept at each study site and updated when the study device is received, opened, implanted, explanted, disposed of, or returned to Medtronic. If the delegated site study team member does not have direct access to the study database, a paper worksheet may be utilized to document device use prior to entering data into the database. In addition to tracking the date of events, the device accountability log tracks product information including, but not limited to, device lot number, date received and expiration date for the product, subject ID of the implanted subject, reason(s) for and method of destruction/disposal for explanted components not returned to Medtronic (if applicable), and name of the person responsible for return or destruction/disposal (if applicable).

Medtronic will perform periodic reconciliation of the study devices to ensure traceability.

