 - Tack, mesh, and other fixation data
- Obtain surgeon satisfaction questionnaire
- Assess and report adverse events, device deficiencies, and study deviations, if applicable

As mentioned, if a subject no longer meets eligibility criteria during the procedure, the patient will be considered an intraoperative screen failure, and no AEs will be reported. For enrolled patients, adverse event and device deficiency collection begins at the time the skin incision is made. Only the specific medications need to be reported, and only for those specific medications that were taken within 30 days of the procedure.

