11.4 Risk-Benefit Rationale

As described in the IFU for the MaxTack[™] Motorized Fixation Device, a ventral hernia repair procedure involving a tacker involves risk. These complications are associated with both the procedure itself as well as the devices being used. For patients who are candidates for the study, the benefits of using the MaxTack[™] Motorized Fixation Device during their hernia repair procedure may outweigh these risks.

In conclusion, the MaxTack[™] Motorized Fixation Device has been shown to have a favorable benefit-risk profile based on the criteria of the target population and the risks and benefits potentials of the device.

12. Adverse Events and Device Deficiencies

For enrolled subjects, adverse events (AE) and device deficiencies (DD) will be collected from the time of skin incision until the subject exits. If an AE is considered unresolvable by the investigator, it will be documented within the eCRF that the AE remains unresolved or unrecovered at the time of study exit. Initial reporting of AEs or DDs may be done by phone, email, or by completing as much information as possible on the appropriate eCRF. The completed AE or DD eCRF must be submitted to Medtronic as soon as possible.

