12.2 Device Deficiency

The device deficiency (DD) definition is provided in Table 5: Adverse Event and Device Deficiency Definitions. DD information will be collected throughout the study and reported to Medtronic. Note that a DD that resulted in an AE to the subject should be captured as an AE only.

AFFIX (MaxTack [™] Motorized Fixation Device) Clinical Investigation Plan				
MDT23014	Revision	3.0	Page 50 of 97	Medtronic

In the event of a DD, the device should be returned to Medtronic for analysis, if possible. Instructions for returning the study device will be provided. Device deficiencies should also be documented in the subject's medical record.

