12.4 Reporting of Adverse Events and Device Deficiencies

Investigators should assess and report the appropriate information on the AE eCRF for the following events, starting from the point of skin incision until the subject exits the study:

- o All AEs related to the MaxTack[™] Motorized Fixation Device, mesh, or study procedure
- o All events that lead to death, regardless of relatedness
- Any non-subject adverse event

Reporting requirements are noted in Section 12.3.1. Assessment of events will include date of event, relationship to study device, relationship to mesh, relationship to study procedure, description, seriousness, action(s) taken, date of resolution and outcome. Additionally, any medication/treatment administered to resolve an AE must also be reported.

Subject Status AE Reporting		AEs to Report Timeframe		
	Required			
Preoperative Screen failure	No	N/A		
Intraoperative Screen failure	No	N/A		
Enrolled	Yes	From skin incision through Study Exit (e.g., study completion, withdrawal or LTFU)		

 Table 7: Subject Status Adverse Event Reporting

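### The stated start of device-deficiency collection (skin incision) is narrower than the deficiency endpoint (the day of the index procedure), so a MaxTack fault found before incision could go uncollected

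*Protocol*

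**What the plan says.** **Endpoint window.** Protocol 5.2.2 lists the incidence of MaxTack deficiencies, with examples ending "tacker issue battery etc.) on day of the index procedure". The Synopsis has the same endpoint, ending "tacker battery issue, etc.) on the day of the index procedure". Neither limits the window to the time after incision.

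**Collection window.** Section 10.7 states: "For enrolled patients, adverse event and device deficiency collection begins at the time the skin incision is made". The opening of Section 12 agrees: "For enrolled subjects, adverse events (AE) and device deficiencies (DD) will be collected from the time of skin incision until the subject exits". The lead-in to 12.4 uses the same start, "starting from the point of skin incision until the subject exits the study", although the list below it names adverse events only. Table 3 marks deficiency evaluation on the Operative Day and refers to Section 12 for the requirements.

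**Text with no incision limit.** Section 12.2 says: "DD information will be collected throughout the study and reported to Medtronic". In the Synopsis safety row, the incision limit sits in the sentence on adverse events, and a separate sentence then says that any device deficiency is collected.

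**Related records.** The 7.7 accountability log is to be "updated when the study device is received, opened, implanted, explanted, disposed of, or returned to Medtronic". Section 12.6 requires product complaints to be reported through the usual market channels. Neither is named as a source for the endpoint.

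**The concern.** Skin incision is a natural start for harm to a subject. It is a less natural start for a fault in a device, which can show without any contact with the patient. MaxTack runs on two batteries and signals its status by light and sound (7.1). It is supplied sealed in a tray and pouch (7.3). The deficiency definition in Table 5 includes malfunctions and inadequate labelling. Some such faults could be noticed when the device is unpacked or started.

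If that happens before incision, and the unit is replaced by a second MaxTack with which the case is completed, the subject meets the enrolment definition in 10.6.1 and enters the analysis set. Under the stated start time that subject would count as having no deficiency, although the fault occurred on the index day. Any such error can only lower the reported incidence. Because the Protocol's statements on the window differ, sites could also apply different rules to the same endpoint.

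**Working it through.** **1. The windows side by side.**

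| Source (Protocol) | Window for deficiencies |
|---|---|
| 5.2.2 and Synopsis endpoint | Day of the index procedure |
| 10.7 | From skin incision, enrolled subjects |
| Section 12, opening | From skin incision to exit, enrolled subjects |
| Table 3 | Operative Day; refers to Section 12 |
| 12.2 | Throughout the study; no start point |
| Synopsis safety row | Any deficiency; no start point |

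Only 10.7 and the opening of Section 12 say when deficiency collection starts, and both say incision. The part of the index day before incision is therefore in the endpoint but not in the stated collection period.

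**2. Size per missed subject.** The Protocol gives no expected deficiency rate and no rate of pre-incision faults, so there is no planned figure to reproduce for this endpoint. With about 110 enrolled (14.6), one missed subject is 1/110 = 0.91 percentage points.

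**3. Effect on the interval, for illustration.** Assume that no deficiency is recorded and that k subjects had a pre-incision fault that was missed. The exact 95% upper limit is 1 − 0.025^(1/110) for k = 0. For k > 0 it is the 0.975 quantile of Beta(k + 1, 110 − k).

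| Missed subjects k | Incidence | Upper 95% limit |
|---|---|---|
| 0 | 0.00% | 3.30% |
| 1 | 0.91% | 4.96% |
| 2 | 1.82% | 6.41% |
| 3 | 2.73% | 7.76% |

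**4. Chance of losing at least one, under assumed rates.** With p the probability per subject of a fault that appears before incision and is not reported, the chance is 1 − (1 − p)^110. It is 0 for p = 0, 42% for p = 0.5%, 67% for p = 1% and 89% for p = 2%. These values of p are assumptions; the Protocol supports none of them over zero.

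**5. The primary analysis.** The stated design reproduces:
- Exact upper limit for 3 of 100: 8.52%, below 8.6%. For 4 of 100 it is 9.93%.
- Probability of 3 or fewer recurrences in 100 at a true rate of 1.0%: 98.2%, consistent with the stated power of over 90%.
- Probability of 3 or fewer at a true rate of 8.6%: 0.0235, below 0.025.
- Enrolment: 100/(1 − 0.09) = 109.9, rounded up to 110.

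None of these uses the deficiency data.

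**The case against.** **The mechanism is assumed.** No section says that a MaxTack is opened, powered or checked before incision. The shaft goes through a cannula to fix mesh (7.1), so opening after incision is at least as plausible. Most of the endpoint's examples (poor penetration, loose tacks, migration) are failures in use, and a battery fault may also show only on firing. This stands: the loss may be zero.

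**Exclusion is not settled.** A reader might infer that pre-incision faults are definitely not counted and that the deficiency rate is therefore biased downward. The Protocol does not support that. Section 12.2 and the Synopsis safety row have no incision limit, and 10.7 itself makes deficiency assessment an operative-day task. What stands is an inconsistency. The general statements do not clearly override two explicit start times, and a site following 10.7 to the letter would omit these faults.

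**The sponsor would still hear of the fault.** The complaint route in 12.6 has no incision limit, and 7.7 logs every opened device. A reader might infer a gap in safety surveillance, and these provisions argue against that. They do not close the endpoint gap, because neither feeds the endpoint as written.

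**The endpoint is minor.** It is descriptive, with no performance goal or test (14.5, 14.8). This stands and limits the weight of the point.

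**Other restrictions are explicit.** Deficiencies in intraoperative screen failures are not reported (10.14.2), and a deficiency that causes an adverse event is recorded only as an adverse event (12.2). Those are separate stated rules, and changing the start time would not affect them.

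**Conclusion.** The point holds as a mismatch between the endpoint window and the stated collection start, with other parts of the Protocol leaving the start open. If collection follows 10.7 and the opening of Section 12, a MaxTack fault found before incision in a later-enrolled subject would not be collected, and the descriptive incidence could be understated.

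The size is 0.91 percentage points of 110 per missed subject. The number missed is unknown and may be zero. A loss requires that a device is opened or started before incision, that a fault shows then, that the subject is still enrolled, and that the site applies the incision start literally. The Protocol establishes none of the first three as expected events. The primary conclusion of the study does not depend on this. The change is still worth making because the possible error runs in one direction and the correction is cheap.

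**What to change.** In 10.7 and the opening of Section 12, separate the two start times:
- Keep skin incision as the start for adverse events.
- Start MaxTack deficiency collection when a MaxTack is opened for the subject on the Operative Day.

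Bring the lead-in to 12.4 and the wording of 12.2 and the Synopsis safety row into line, so that one rule applies throughout. Keep the endpoint as a subject-level incidence: enrolled subjects with at least one MaxTack deficiency on the index day, divided by enrolled subjects. Do not turn it into a count of devices. Use the opened-device entries in the 7.7 log only to check that no deficiency report is missing.

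The cost is one sentence in each of two sections, minor alignment elsewhere, and an adjustment to the deficiency form. The accountability entries are already required. The only downside is that the reported incidence may be slightly less favourable.

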10.8 Discharge Visit

The following assessments are required to be performed prior to subject discharge:

- Medication assessment (anticoagulants, antiplatelets, antithrombotic, and/or pain medications)
- Obtain date discharged from hospital (length of hospital stay)
- Assess and report adverse events, device deficiencies, and protocol deviations, if applicable

10.9 Month 1 (+21 Days), 3 (+30 Days), and 12 Follow-up Visits (+45 Days)

The following assessments are required at the Month 1, 3, and 12 follow-up visits:

AFFIX (MaxTa Clinical Invest				
MDT23014	Revision	3.0	Page 42 of 97	Medtronic

- Obtain pain score (Numerical Rating Scale (NRS)) at Hernia Site
- Obtain HerQLes Quality of Life Questionnaire Postoperative Assessment
- Medication assessment (anticoagulants, antiplatelets, antithrombotic, and/or pain medication)
- Clinical assessment, which includes a Valsalva maneuver during clinical physical examination for hernia recurrence, hernia recurrences resulting in reoperation, if applicable
- Assess and report adverse events, device deficiencies, and protocol deviations, if applicable

All visits are to be completed in person. If subjects are unable or unwilling to be seen in person, unforeseen beyond the investigator's control, upon approval by Medtronic, subjects may be given the option to complete the HerQLes Quality of Life questionnaire, provide their pain score, and conduct an AE and medication assessment as well as assess the status any potential hernia recurrence and/or reoperation remotely. In these cases, a study deviation will need to be completed for not being able to perform the required assessments in person.

If a hernia or hernia recurrence is suspected, the subject will be instructed to return to the clinic or hospital for diagnosis by the surgeon through clinical assessment. This should be done at the discretion of the investigator.

10.10 Unscheduled Follow-up Visits

If a subject must be seen by a physician for a study-related adverse event or concern outside of the study follow-up visit schedule, an unscheduled visit form within the database must be completed. The assessments below should be performed at unscheduled follow-up visits. Should the subject see a physician who is not delegated to the study, the information should be obtained from the medical records.

- Visit reason
- Medication assessment (anticoagulants, antiplatelets, antithrombotic, and/or pain medication)
- Details of hernia recurrence/reoperation, if applicable
- Assess and report adverse events, device deficiencies, and protocol deviations, if applicable

10.11 Questionnaires

HerQLes Quality of Life Questionnaire

The HerQLes quality of life questionnaire (QoL) is a hernia-specific survey tool with a focus on abdominal wall function ^{(10-11),} which will be used throughout the study. Subjects will complete the preoperative assessment at screening and the postoperative assessments at Months 1, 3, and 12. See Section 18.4: Appendix D – HerQLes Quality of Life Questionnaire. Prior to site activation, the applicable site personnel will be trained on the requirements for properly administering the QoL questionnaires to subjects.

Subjects should complete QoL questionnaires in the language of their understanding. Generally, the language version of a subject's QoL questionnaire should be the same as the subject's informed consent. If the language version of the subject's QoL questionnaire differs from the subject's informed consent, it is recommended that an explanation be documented (e.g., the subject consented via a translator).

AFFIX (MaxTa Clinical Invest				
MDT23014	Revision	3.0	Page 43 of 97	Medtronic

Subjects should complete their own QoL questionnaires. If the subject needs assistance completing their own QoL questionnaire (e.g., physical limitations), an appropriately authorized person may assist (e.g., reading questions to the subjects and completing the QoL questionnaire on their behalf). Any assistance should be recorded on the QoL questionnaire or applicable source documentation.

The completed QoL questionnaire should include the subject identifier, the associated visit (e.g., 6-month visit), and the visit date.

Surgeon Satisfaction Questionnaire

After each procedure, the operating physician must complete the Surgeon Satisfaction Questionnaire. The Surgeon Satisfaction Questionnaire is a short survey to evaluate the surgeon's use and satisfaction of MaxTack[™] (Section 18.8: Appendix H – Surgeon Satisfaction Questionnaire).

Pain Numerical Rating Scale (NRS)

Subject Pain Numerical Rating Scale (NRS) (Appendix C – Pain Numerical Rating Scale (NRS)) will be collected at follow-up visits per Section 10.1. The Pain NRS requires the patient to choose a number on a defined scale between 0–10, where 0 is no pain, and 10 is the worst possible pain.

An appropriately authorized person will assist with data collection (e.g., verbally reading questions to the subjects and completing the source document on their behalf).

Completed subject NRSs should include the subject identifier, the associated visit (e.g., 3-month visit, 6-month visit), and the visit date.

10.12 Recording Data

This study will utilize an electronic database and eCRFs. Study visits or assessments not collected or recorded will be considered deviations unless otherwise specified. The Principal Investigator or authorized designee(s) must ensure the accuracy and completeness of the recorded data. Once completed, investigators will sign off on (approve) their study data via electronic approval of the eCRFs.

Data entered must be traceable to source documents. Source documentation is defined as all information in original records and certified copies of original records of clinical findings, observations, or other activities in a clinical investigation necessary for the reconstruction and evaluation of the clinical investigation (e.g., hospital records, clinical and office charts, procedure reports, laboratory notes, subject files, subject questionnaires, device data, and copies, or transcriptions certified after verification as being accurate copies).

In general, eCRFs may not serve as source documents. Depending on the study site, the exceptions may be as follows: Surgeon Satisfaction Questionnaire, adverse event seriousness and relationship, device deficiency classifications, and protocol deviation assessments. The study site may use source document worksheets if they are identified as source documents.

	MaxTack [™] Motori Investigation Pla			
MDT23014	Revision	3.0	Page 44 of 97	Medtronic

The investigator must ensure the availability of source documents from which the information on the eCRFs was derived. The type and location of source documents should be documented. Where printouts of electronic medical records are provided as source documents or copies of source documents are retained as source documents, those should be certified as indicated by a dated signature by a member of the investigation site team unless generated through a validated process.

The source documents must be made available for monitoring or auditing by Medtronic's representative or representatives of applicable regulatory agencies.

